## 5.2 Trial Treatment(s)

The treatment to be used in this trial is outlined below in [Table 2](#).

Table 2 Trial Treatment

Drug, Vaccine, Biologic, Device, etc.	Dose/Potency	Dose Frequency	Route of Administration	Regimen/Treatment Period/Vaccination Regimen	Use
pembrolizumab (MK-3475)	200 mg	Q3W	IV infusion	Day 1 of each 3 week cycle	Experimental

Trial treatment should begin on the day of randomization or as close as possible to the date on which the subject is allocated/assigned.

The investigator shall take responsibility for and shall take all steps to maintain appropriate records and ensure appropriate supply, storage, handling, distribution and usage of trial treatments in accordance with the protocol and any applicable laws and regulations.

## **5.2.1 Dose Modification (Escalation/Titration/Other)**

### **5.2.1.1 Dose Selection (Preparation)**

The rationale for selection of doses to be used in this trial is provided in Section 4.0 – Background & Rationale. Details on preparation and administration of pembrolizumab (MK-3475) are provided in the Pharmacy Manual.

### **5.2.1.2 Immune-Related Events and Dose Modification (Withhold, Treat, Discontinue)**

#### **Dose Modification and Toxicity Management for Immune-related AEs Associated with Pembrolizumab**

AEs associated with pembrolizumab exposure may represent an immune-related response. These irAEs may occur shortly after the first dose or several months after the last dose of pembrolizumab treatment and may affect more than one body system simultaneously. Therefore, early recognition and initiation of treatment is critical to reduce complications. Based on existing clinical study data, most irAEs were reversible and could be managed with interruptions of pembrolizumab, administration of corticosteroids and/or other supportive care. For suspected irAEs, ensure adequate evaluation to confirm etiology or exclude other causes. Additional procedures or tests such as bronchoscopy, endoscopy, skin biopsy may be included as part of the evaluation. Based on the severity of irAEs, withhold or permanently discontinue pembrolizumab and administer corticosteroids.

Dose Modification and Toxicity Management Guidelines for irAEs associated with pembrolizumab monotherapy, coformulations, or IO combinations are provided in [Table 3](#).

**Table 3 Dose Modification and Toxicity Management Guidelines for Immune-related Adverse Events Associated with Pembrolizumab Monotherapy, Coformulations or IO Combinations**

General instructions:
 
 
1. Severe and life-threatening irAEs should be treated with IV corticosteroids followed by oral steroids. Other immunosuppressive treatment should begin if the irAEs are not controlled by corticosteroids.
 
2. Pembrolizumab monotherapy, coformulations or IO combinations must be permanently discontinued if the irAE does not resolve or the corticosteroid dose is not <math>\leq 10</math> mg/day within 12 weeks of the last treatment.
 
3. The corticosteroid taper should begin when the irAE is <math>\leq</math> Grade 1 and continue at least 4 weeks.
 
4. If pembrolizumab monotherapy, coformulations or IO combinations have been withheld, treatment may resume after the irAE decreased to <math>\leq</math> Grade 1 after corticosteroid taper.
 
				
irAEs	Toxicity Grade (CTCAEv4.0)	Action With Pembrolizumab Monotherapy, Coformulations or IO Combinations	Corticosteroid and/or Other Therapies	Monitoring and Follow-up
Pneumonitis	Grade 2	Withhold	
 
• Administer corticosteroids (initial dose of 1-2 mg/kg prednisone or equivalent) followed by taper
 
	
 
• Monitor participants for signs and symptoms of pneumonitis
 
• Evaluate participants with suspected pneumonitis with radiographic imaging and initiate corticosteroid treatment
 
• Add prophylactic antibiotics for opportunistic infections
 

	Recurrent Grade 2 or Grade 3 or 4	Permanently discontinue		
Diarrhea / Colitis	Grade 2 or 3	Withhold	
 
• Administer corticosteroids (initial dose of 1-2 mg/kg prednisone or equivalent) followed by taper
 
	
 
• Monitor participants for signs and symptoms of enterocolitis (ie, diarrhea, abdominal pain, blood or mucus in stool with or without fever) and of bowel perforation (ie, peritoneal signs and ileus)
 
• Participants with <math>\geq</math>Grade 2 diarrhea suspecting colitis should consider GI consultation and performing endoscopy to rule out colitis
 
• Participants with diarrhea/colitis should be advised to drink liberal quantities of clear fluids. If sufficient oral fluid intake is not feasible, fluid and electrolytes should be substituted via IV infusion.
 

	Recurrent Grade 3 or Grade 4	Permanently discontinue		

irAEs	Toxicity Grade (CTCAEv4.0)	Action With Pembrolizumab Monotherapy, Coformulations or IO Combinations	Corticosteroid and/or Other Therapies	Monitoring and Follow-up
AST / ALT Elevation or Increased Bilirubin	Grade 2	Withhold	
 
Administer corticosteroids (initial dose of 0.5-1 mg/kg prednisone or equivalent) followed by taper
 
	
 
Monitor with liver function tests (consider weekly or more frequently until liver enzyme value returned to baseline or is stable)
 

	Grade 3 or 4	Permanently discontinue	
 
Administer corticosteroids (initial dose of 1-2 mg/kg prednisone or equivalent) followed by taper
 
	
T1DM or Hyperglycemia	New onset T1DM or Grade 3 or 4 hyperglycemia associated with evidence of $\beta$ -cell failure	Withhold a	
 
Initiate insulin replacement therapy for participants with T1DM
 
Administer anti-hyperglycemic in participants with hyperglycemia
 
	
 
Monitor participants for hyperglycemia or other signs and symptoms of diabetes
 

Hypophysitis	Grade 2	Withhold	
 
Administer corticosteroids and initiate hormonal replacements as clinically indicated
 
	
 
Monitor for signs and symptoms of hypophysitis (including hypopituitarism and adrenal insufficiency)
 

	Grade 3 or 4	Withhold or permanently discontinue a		
Hyperthyroidism	Grade 2	Continue	
 
Treat with non-selective beta-blockers (eg, propranolol) or thionamides as appropriate
 
	
 
Monitor for signs and symptoms of thyroid disorders
 

	Grade 3 or 4	Withhold or Permanently discontinue a		

irAEs	Toxicity Grade (CTCAEv4.0)	Action With Pembrolizumab Monotherapy, Coformulations or IO Combinations	Corticosteroid and/or Other Therapies	Monitoring and Follow-up
Hypothyroidism	Grade 2-4	Continue	
 
Initiate thyroid replacement hormones (eg, levothyroxine or liothyronine) per standard of care
 
	
 
Monitor for signs and symptoms of thyroid disorders
 

Nephritis and renal dysfunction	Grade 2	Withhold	
 
Administer corticosteroids (prednisone 1-2 mg/kg or equivalent) followed by taper
 
	
 
Monitor changes of renal function
 

	Grade 3 or 4	Permanently discontinue		
Myocarditis	Grade 1	Withhold	
 
Based on severity of AE administer corticosteroids
 
	
 
Ensure adequate evaluation to confirm etiology and/or exclude other causes
 

	Grade 2, 3 or 4	Permanently discontinue		
All Other irAEs	Persistent Grade 2	Withhold	
 
Based on severity of AE administer corticosteroids
 
	
 
Ensure adequate evaluation to confirm etiology or exclude other causes
 

	Grade 3	Withhold or discontinue b		
	Recurrent Grade 3 or Grade 4	Permanently discontinue		

AE(s)=adverse event(s); ALT= alanine aminotransferase; AST=aspartate aminotransferase; CTCAE=Common Terminology Criteria for Adverse Events; DRESS=Drug Rash with Eosinophilia and Systemic Symptom; GI=gastrointestinal; IO=immuno-oncology; ir=immune related; IV=intravenous; SJS=Stevens-Johnson Syndrome; T1DM=type 1 diabetes mellitus; TEN=Toxic Epidermal Necrolysis; ULN=upper limit of normal.
 
Note: Non-irAE will be managed as appropriate, following clinical practice recommendations.
 
a The decision to withhold or permanently discontinue pembrolizumab monotherapy, coformulations or IO combinations is at the discretion of the investigator or treating physician. If control achieved or ≤ Grade 2, pembrolizumab monotherapy, coformulations or IO combinations may be resumed.
 
b Events that require discontinuation include, but are not limited to: Guillain-Barre Syndrome, encephalitis, myelitis, DRESS, SJS, TEN and other clinically important irAEs (eg, vasculitis and sclerosing cholangitis).
				

**Dose modification and toxicity management of infusion-reactions related to pembrolizumab**

Pembrolizumab may cause severe or life threatening infusion-reactions including severe hypersensitivity or anaphylaxis. Signs and symptoms usually develop during or shortly after drug infusion and generally resolve completely within 24 hours of completion of infusion. Dose modification and toxicity management guidelines on pembrolizumab associated infusion reaction are provided in [Table 4](#).

Table 4 Pembrolizumab Infusion Reaction Dose modification and Treatment Guidelines

NCI CTCAE Grade	Treatment	Premedication at Subsequent Dosing

Grade 1                      Mild reaction; infusion interruption not indicated; intervention not indicated
	
Increase monitoring of vital signs as medically indicated until the subject is deemed medically stable in the opinion of the investigator.
	
None

Grade 2                      Requires therapy or infusion interruption but responds promptly to symptomatic treatment (e.g., antihistamines, NSAIDs, narcotics, IV fluids); prophylactic medications indicated for ≤24 hrs
	
Stop Infusion.                      Additional appropriate medical therapy may include but is not limited to:                      IV fluids                      Antihistamines                      NSAIDs                      Acetaminophen                      Narcotics
 
Increase monitoring of vital signs as medically indicated until the subject is deemed medically stable in the opinion of the investigator.
 
If symptoms resolve within 1 hour of stopping drug infusion, the infusion may be restarted at 50% of the original infusion rate (e.g. from 100 mL/hr to 50 mL/hr). Otherwise dosing will be held until symptoms resolve and the subject should be premedicated for the next scheduled dose.
 
Subjects who develop Grade 2 toxicity despite adequate premedication should be permanently discontinued from further study drug treatment
	
Subject may be premedicated 1.5h (± 30 minutes) prior to infusion of pembrolizumab with:                      Diphenhydramine 50 mg po (or equivalent dose of antihistamine).                      Acetaminophen 500-1000 mg po (or equivalent dose of analgesic).

NCI CTCAE Grade	Treatment	Premedication at Subsequent Dosing

Grades 3 or 4
 
Grade 3: Prolonged (i.e., not rapidly responsive to symptomatic medication and/or brief interruption of infusion); recurrence of symptoms following initial improvement; hospitalization indicated for other clinical sequelae (e.g., renal impairment, pulmonary infiltrates)
 
Grade 4: Life-threatening; pressor or ventilatory support indicated
	
Stop Infusion.
 
Additional appropriate medical therapy may include but is not limited to:
 
Epinephrine**            IV fluids            Antihistamines            NSAIDs            Acetaminophen            Narcotics            Oxygen            Pressors            Corticosteroids
 
Increase monitoring of vital signs as medically indicated until the subject is deemed medically stable in the opinion of the investigator.
 
Hospitalization may be indicated.
 
**In cases of anaphylaxis, epinephrine should be used immediately.
 
Subject is permanently discontinued from further study drug treatment.
	
No subsequent dosing

Appropriate resuscitation equipment should be available at the bedside and a physician readily available during the period of drug administration.
 
For further information, please refer to the Common Terminology Criteria for Adverse Events v4.0 (CTCAE) at http://ctep.cancer.gov
		

**Other allowed dose interruption for pembrolizumab**

Pembrolizumab may be interrupted for situations other than treatment-related AEs such as medical / surgical events or logistical reasons not related to study therapy. Subjects should be placed back on study therapy within 3 weeks of the scheduled interruption, unless otherwise discussed with the Sponsor. The reason for interruption should be documented in the subject's study record.

**5.2.2 Timing of Dose Administration**

Trial treatment should be administered on Day 1 of each cycle after all procedures/assessments have been completed as detailed on the Trial Flow Chart (Section 6.0). Trial treatment may be administered up to 3 days before or after the scheduled Day 1 of each cycle due to administrative reasons. Trial treatments will be administered on an outpatient basis, unless the subject is hospitalized for an unrelated reason. Pembrolizumab (MK-3475)

Pembrolizumab (MK-3475) 200 mg will be administered as a 30 minute IV infusion every 3 weeks. Treatment cycle intervals may be increased due to toxicity as described in Section 5.2.1.2. Sites should make every effort to target infusion timing to be as close to 30 minutes as possible. However, given the variability of infusion pumps from site to site, a window of -5 minutes and +10 minutes is permitted (i.e., infusion time is 30 minutes: -5 min/+10 min).

The Pharmacy Manual contains specific instructions for pembrolizumab (MK-3475) dose calculation, reconstitution, preparation of the infusion fluid, and administration.

### **5.2.3 Trial Blinding/Masking**

This is an open-label trial; therefore, the Sponsor, investigator and subject will know the treatment administered.

### **5.3 Randomization or Treatment Allocation**

Randomization will occur centrally using an interactive voice response system / integrated web response system (IVRS/IWRS). Subjects will be assigned to pembrolizumab (MK-3475) in an unblinded fashion.

Subjects participating in this trial will be allocated by non-random assignment.

### **5.4 Stratification**

No stratification based on age, sex or other characteristics will be used in this trial.

### **5.5 Concomitant Medications/Vaccinations (Allowed & Prohibited)**

Medications or vaccinations specifically prohibited in the exclusion criteria are not allowed during the ongoing trial. If there is a clinical indication for any medication or vaccination specifically prohibited during the trial, discontinuation from trial therapy or vaccination may be required. The investigator should discuss any questions regarding this with the Sponsor Clinical Director. The final decision on any supportive therapy or vaccination rests with the investigator and/or the subject's primary physician. However, the decision to continue the subject on trial therapy or vaccination schedule requires the mutual agreement of the investigator, the Sponsor and the subject.

#### **5.5.1 Acceptable Concomitant Medications**

All treatments that the investigator considers necessary for a subject's welfare may be administered at the discretion of the investigator in keeping with the community standards of medical care. All concomitant medication will be recorded on the case report form (CRF) including all prescription, over-the-counter (OTC), herbal supplements, and IV medications and fluids. If changes occur during the trial period, documentation of drug dosage, frequency, route, and date may also be included on the CRF.

All concomitant medications received within 30 days before the first dose of trial treatment and 30 days after the last dose of trial treatment should be recorded. Concomitant medications administered after 30 days after the last dose of trial treatment should be recorded for SAEs and ECIs as defined in Section 7.2.

### **5.5.2 Prohibited Concomitant Medications**

Subjects are prohibited from receiving the following therapies during the Screening and Treatment Phase (including retreatment for post-complete response relapse) of this trial:

- Antineoplastic systemic chemotherapy or biological therapy
- Immunotherapy not specified in this protocol
- Chemotherapy not specified in this protocol
- Investigational agents other than pembrolizumab (MK-3475)
- Radiation therapy
  - Note: Radiation therapy to a symptomatic solitary lesion or to the brain may be allowed after consultation with Sponsor.
- Live vaccines within 30 days prior to the first dose of trial treatment and while participating in the trial. Examples of live vaccines include, but are not limited to, the following: measles, mumps, rubella, varicella/zoster, yellow fever, intranasal influenza, rabies, BCG, and typhoid vaccine.
- Systemic glucocorticoids for any purpose other than to modulate symptoms from an event of clinical interest of suspected immunologic etiology. Subjects who require corticosteroids to manage drug-related adverse events must be at an equivalent dose of  $\leq 10$  mg per day of prednisone to resume dosing with MK-3475. Furthermore, an inability to reduce the corticosteroid dose for managing a drug-related adverse event to the equivalent of  $\leq 10$  mg prednisone per day within 12 weeks of last MK-3475 dose should prompt discussion between the investigator and Sponsor regarding the subject's ability to continue on treatment in the trial.
  - Note: Temporary use of prophylactic corticosteroids to avoid allergic reactions (e.g. IV contrast dye or transfusions) is permitted.
  - Note: Use of intermittent inhaled steroids or local injection of corticosteroids is permitted upon consultation with the sponsor.

Subjects who, in the assessment by the investigator, require the use of any of the aforementioned treatments for clinical management should be removed from the trial.

Subjects may receive other medications that the investigator deems to be medically necessary.

The Exclusion Criteria describes other medications, which are prohibited in this trial.

There are no prohibited therapies during the Post-Treatment Follow-up Phase.

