### **5.7.3 Use in Pregnancy**

If a subject inadvertently becomes pregnant while on treatment with pembrolizumab (MK-3475), the subject will immediately be removed from the study. The site will contact the subject at least monthly and document the subject's status until the pregnancy has been completed or terminated. The outcome of the pregnancy will be reported to the Sponsor without delay and within 24 hours if the outcome is a serious adverse experience (e.g., death, abortion, congenital anomaly, or other disabling or life-threatening complication to the mother or newborn). The study investigator will make every effort to obtain permission to follow the outcome of the pregnancy and report the condition of the fetus or newborn to the Sponsor. If a male subject impregnates his female partner the study personnel at the site must be informed immediately and the pregnancy reported to the Sponsor and followed as described above and in Section 7.2.2.

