## **5.8 Subject Withdrawal/Discontinuation Criteria**

Subjects may withdraw consent at any time for any reason or be dropped from the trial at the discretion of the investigator should any untoward effect occur. In addition, a subject may be withdrawn by the investigator or the Sponsor if enrollment into the trial is inappropriate, the trial plan is violated, or for administrative and/or other safety reasons. Specific details regarding discontinuation or withdrawal procedures; including specific details regarding

withdrawal from Future Biomedical Research, are provided in Section 7.1.4 – Other Procedures.

In this trial, a subject may discontinue from treatment but continue to participate in the regularly scheduled activities, as long as the subject does not withdraw consent. Once a subject has discontinued treatment, even though he/she continues to be monitored in the trial, he/she may be allowed to begin treatment again if deemed medically appropriate.

A subject must be discontinued from the trial for any of the following reasons:

- The subject or legal representative (such as a parent or legal guardian) withdraws consent.

A subject must be discontinued from treatment (but may continue to be monitored in the trial) for any of the following reasons:

- The subject or legal representative (such as a parent or legal guardian) withdraws consent for treatment
- Confirmed radiographic disease progression

*Note:* For unconfirmed radiographic disease progression, please see Section 5.8.1.

*Note:* A subject may be granted an exception to continue on treatment with confirmed radiographic progression if clinically stable or clinically improved, please see Section 5.8.1 below.

- Unacceptable adverse experiences as described in Section 5.2.1.2
- Intercurrent illness that prevents further administration of treatment
- Investigator’s decision to withdraw the subject
- The subject has a confirmed positive serum pregnancy test
- Noncompliance with trial treatment or procedure requirements
- The subject is lost to follow-up
- Completed 24 months of treatment with pembrolizumab (MK-3475)

*Note:* 24 months of study medication is calculated from the date of first dose. Subjects who stop pembrolizumab (MK-3475) after 24 months may be eligible for up to one year of additional study treatment if they progress after stopping study treatment provided they meet the requirements detailed in Section 7.1.5.2.1.

- Administrative reasons

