#### **7.1.1.5.2.1 Subsequent Anti-Cancer Therapy Status**

The investigator or qualified designee will review all new anti-cancer therapy initiated after the last dose of trial treatment. If a subject initiates a new anti-cancer therapy within 30 days after the last dose of trial treatment, the 30 day Safety Follow-up visit must occur before the first dose of the new therapy. Once new anti-cancer therapy has been initiated the subject will move into survival follow-up.

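### Section 5.5.2 removes subjects who need a prohibited therapy from the trial, against the plan's own survival follow-up rules; applied literally, it could overstate OS

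*Combined protocol and SAP*

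**What the plan says.** Section 5.5.2 lists therapies prohibited during the Screening and Treatment Phase: antineoplastic, immune and investigational therapy, radiation, live vaccines, and systemic glucocorticoids outside a stated purpose. Subjects who, in the investigator's assessment, "require the use of any of the aforementioned treatments for clinical management should be removed from the trial".

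Other sections treat the same or overlapping situations differently:

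- **Section 5.5**, the parent section: if a prohibited medication is clinically indicated, "discontinuation from trial therapy or vaccination may be required". It does not mention leaving the trial.
- **Section 5.8** separates leaving the trial from stopping treatment. One mandatory reason for leaving is listed: "The subject or legal representative (such as a parent or legal guardian) withdraws consent". The longer list opens with "A subject must be discontinued from treatment (but may continue to be monitored in the trial) for any of the following reasons". In general, "a subject may discontinue from treatment but continue to participate in the regularly scheduled activities, as long as the subject does not withdraw consent". The same section also allows discretionary withdrawal: "a subject may be withdrawn by the investigator or the Sponsor if enrollment into the trial is inappropriate, the trial plan is violated".
- **Section 7.1.1.5.2.1**: "Once new anti-cancer therapy has been initiated the subject will move into survival follow-up".
- **Section 2.1** provides for telephone survival follow-up of all subjects every 12 weeks until death, withdrawal of consent or the end of the trial. **Section 7.1.5.3.3** applies survival follow-up to anyone who stops trial treatment.

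OS and PFS, with 6- and 12-month rates, are secondary objectives (Section 3.2). Table 8 censors both at the last assessment. Section 5.7.3 has wording like that of 5.5.2 for pregnancy ("the subject will immediately be removed from the study"), whereas 5.8 lists a positive pregnancy test under stopping treatment.

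**The concern.** A subject who needs chemotherapy during the treatment phase falls under two instructions: removal from the trial (5.5.2) and transfer to survival follow-up (7.1.1.5.2.1). Removal has practical consequences. Under Section 7.1.4.1, a subject who discontinues participation completes the final-visit activities at that point, so a site reading 5.5.2 literally has grounds to stop the survival calls.

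OS would then be censored when the therapy is needed. Kaplan-Meier assumes that a censored subject has the same future hazard as those still at risk. Need for other antineoplastic therapy or radiation often marks worsening disease, so that assumption is doubtful here. The trial has a single arm, so any bias passes directly into the reported median and landmark rates. The plan describes no OS sensitivity analysis for these subjects.

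**Working it through.** The documents state no figure for this point, so there is none to reproduce. The check has two parts.

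**1. The rules side by side**

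| Section | Situation | Instruction |
|---|---|---|
| 5.5.2 | Needs a listed therapy while on treatment | Remove from the trial |
| 5.5 | Prohibited medication clinically indicated | Trial therapy may have to stop |
| 5.8 | Listed reasons; this need is not among them | Stop treatment, monitoring may continue; only withdrawn consent makes leaving mandatory |
| 7.1.1.5.2.1 | Starts new anti-cancer therapy | Survival follow-up |
| 7.1.5.3.3 | Stops trial treatment | Survival follow-up |
| 2.1 | All subjects | Survival calls to death, withdrawn consent or end of trial |

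Section 5.5.2 stands alone. It also says that nothing is prohibited in post-treatment follow-up, so it expects that phase to exist for subjects receiving such therapies.

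**2. Direction and possible size of the OS effect**

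Inputs:

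- True median OS is set at 8.5 months, the middle of the 8 to 9 months that Section 4.2.1 cites for carboplatin regimens. This is an anchor, not a forecast for pembrolizumab.
- f, the share who come to need a prohibited therapy before death, and HR, their death hazard after that point relative to before it, are assumptions. The documents give neither.
- Vital status is assumed to be lost for every removed subject.

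Model: the death hazard is λ before the need arises and HR·λ after it. The rate of moving to that state is μ = λ·f/(1 − f). Write a = λ + μ.

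- True survival: S(t) = exp(−a·t) + μ·[exp(−HR·λ·t) − exp(−a·t)]/(a − HR·λ), with λ solved so that S(8.5) = 0.5.
- Kaplan-Meier with removed subjects censored estimates exp(−λ·t).

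Worked case, f = 20%, HR = 2: λ = 0.07664 per month, μ = 0.07664 × 0.20/0.80 = 0.01916, a = 0.09580 and 2λ = 0.15329.

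- True S(12) = 0.3167 + [0.01916/(0.09580 − 0.15329)] × (0.1589 − 0.3167) = 0.3167 + 0.0526 = 0.369.
- Kaplan-Meier: exp(−0.07664 × 12) = 0.399.
- Bias: +2.9 points. A simulation of 2,000 trials of 350 subjects gave 36.9% against 39.8%.

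Differences below are taken before rounding.

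| f | HR | True 12-month OS | Kaplan-Meier | Bias (points) | Apparent median (true 8.5) |
|---|---|---|---|---|---|
| any | 1 | 37.6% | 37.6% | 0.0 | 8.50 |
| 5% | 2 | 37.4% | 38.1% | +0.7 | 8.62 |
| 5% | 3 | 37.4% | 38.4% | +1.1 | 8.70 |
| 10% | 2 | 37.3% | 38.7% | +1.4 | 8.75 |
| 10% | 3 | 37.2% | 39.3% | +2.1 | 8.92 |
| 20% | 2 | 36.9% | 39.9% | +2.9 | 9.04 |
| 20% | 3 | 36.8% | 41.2% | +4.5 | 9.39 |

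At 6 months the effect is smaller. For f = 20% and HR = 3, Kaplan-Meier reads 64.2% against a true 61.9%, or +2.3 points.

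Fixing the median of the not-yet-removed state at 9 months instead gives similar results: Kaplan-Meier reads 39.7% at 12 months against a true 38.3% (10%, 2x), 36.8% (20%, 2x) and 35.1% (20%, 3x).

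**The case against.** The best counter-argument is that survival follow-up is already secured. Sections 2.1, 7.1.1.5.2.1 and 7.1.5.3.3 all call for it, and Section 7.1.5.4 lets the sponsor ask for survival status on participants without a scheduled contact. Nothing shows that sites would follow one sentence over these. That stands as a limit on likelihood: the harm is conditional. It does not remove the conflict. The sponsor's requests are discretionary, and the plan does not say whether they reach a subject who has been removed.

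Other limits also stand:

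- A reader might infer that Section 5.8 guarantees follow-up for these subjects. It does not. It says monitoring may continue, does not list this situation, and permits discretionary withdrawal. The firmer support is in 2.1, 7.1.1.5.2.1 and 7.1.5.3.3.
- The affected group is narrow and mixed. The rule covers only screening and treatment. Some radiation may be allowed after sponsor consultation and several steroid uses are permitted. A live vaccine need not signal decline.
- For scale, the binomial margin on a 38% rate with 350 subjects is 1.96 × √(0.38 × 0.62/350), about ±5 points. The bias in the table lies within it, although, unlike sampling error, bias does not shrink with more subjects.
- A reader might infer that PFS suffers equally. Scheduled imaging already stops at new anti-cancer treatment (Section 6.1 note b; Sections 7.1.2.6.2, 7.1.2.6.4 and 7.1.5.3.2), so the added loss is mainly in radiation and steroid cases.

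**Conclusion.** The contradiction is real, and the protocol should not leave sites to resolve it. If 5.5.2 is applied literally and the removed subjects do worse, the secondary OS estimates are too high. With 5% to 20% removed and a 2- to 3-fold death hazard, the 12-month rate is overstated by roughly 1 to 5 points and the median by about 0.1 to 0.9 months (8.62 to 9.39 against 8.5). With equal hazards there is no bias. Removal share, hazard ratio and complete loss of vital status are all assumptions.

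Two stronger conclusions are tempting. One is that the trial's OS results are overstated. The documents do not show that any site acts on 5.5.2 in this way, how many subjects it would affect, or that those subjects have a higher hazard. The other is that the primary result is inflated. It is not, because Section 8.2.5.1 counts subjects without response data as non-responders. The pregnancy wording in 5.7.3 is a parallel inconsistency and no source of survival bias; that section also requires at least monthly contact until the pregnancy ends.

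This is worth correcting, but it does not threaten the primary objective.

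**What to change.** Reconcile 5.5.2 with Sections 2.1, 5.8, 7.1.1.5.2.1 and 7.1.5.3.3. State that a subject who falls under 5.5.2 remains in survival follow-up, and in disease follow-up where Section 7.1.5.3.2 applies, unless consent is withdrawn. The sentence should deal with follow-up alone. Whether trial treatment stops in these cases is a clinical rule, and this point neither changes nor proposes one.

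Reconcile the similar wording in 5.7.3 with 5.8 for consistency only.

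The cost is about two sentences in the next amendment or a clarification letter to sites. The 12-weekly calls are already part of the plan, so no new procedure is needed.
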